Clinical Investigation Plan

Document ID: PD-545909 Rev: 01

IRB Approved at the

Protocol Level

Page 1(42) Mat 15, 2019

Title: CIP_MxBFlex_02 with Integrated Central Amendment 1 and 2

Investigation Code **MxBFlex_02** Final Version Approval date **2018-06-19**

Central Amendment 1 Approval date **2018-11-08**

Central Amendment 2 Approval date

[figure not shown]
CLINICAL INVESTIGATION PLAN (CIP)

INVESTIGATIONAL DEVICE:

MEPILEX® BORDER FLEX

INVESTIGATION TITLE:

A PROSPECTIVE, RANDOMIZED, CONTROLLED, STUDY USING CROSS-OVER DESIGN TO EVALUATE AND COMPARE 3 MULTI-LAYERED FOAM DRESSINGS FOR THE MANAGEMENT OF CHRONIC WOUNDS

CO-ORDINATING INVESTIGATOR:

[name] PhD, CCT, FPWCA

SPONSOR

MÖLNLYCKE CLINICAL STUDY

MANAGER:

[name]

Mölnlycke Health Care

[name]

[name]

[contact] xx

[contact]

Clinical Investigation Plan

Document ID: PD-545909 Rev: 01

Title: CIP_MxBFlex_02 with Integrated Central Amendment 1 and 2

Page 2(42)

Investigation Code **MxBFlex_02** Final Version Approval date **2018-06-19**

Central Amendment 1 Approval date **2018-11-08**

Central Amendment 2 Approval date

Investigation Code	MxBFlex_02	Final Version	Approval date	2018-06-19
		Central Amendment 1	Approval date	2018-11-08
		Central Amendment 2	Approval date	

PROTOCOL SYNOPSIS

PROTOCOL TITLE:

A PROSPECTIVE, RANDOMIZED, CONTROLLED STUDY USING CROSS-OVER DESIGN TO EVALUATE AND COMPARE 3 MULTI-LAYERED FOAM DRESSINGS FOR THE MANAGEMENT OF CHRONIC WOUNDS

Clinical Study Site:

Multiple Sites

Investigational Device (test dressings):

Mepilex® Border Flex, Mölnlycke Health Care; Optifoam Gentle EX Wound Dressing, Medline Industries Inc.; Allevyn Life Wound Dressing, Smith and Nephew Inc.

Study Objectives

Primary Objective

To demonstrate superiority in efficacy of Mepilex® Border Flex versus Optifoam Gentle EX and Allevyn Life in the management of venous leg ulcers (VLUs) and diabetic foot ulcers (DFUs) in an outpatient setting, as determined by dressing durability (i.e. wear time).

Secondary Objectives

- To compare clinical wound characteristics during wound management with each of the test dressings (in combination with standard care), including the rate of wound healing, peri-wound skin condition, and local pain levels.
- To evaluate the safety of the three test dressings in terms of occurrence of device related adverse events (AEs).
- To study subject-centric outcomes associated with each of the test dressings.

Health Economics Objective

- To retrospectively compare the cost-effectiveness of the three wound dressings.

Primary Endpoint:

Wound dressing durability, as defined as the interval of time to dressing strike-through and need for dressing change (dressing wear time [days]).

Investigation Code	MxBFlex_02	Final Version	Approval date	2018-06-19
		Central Amendment 1	Approval date	2018-11-08
		Central Amendment 2	Approval date	

Secondary Endpoints:

- Clinical wound characteristics: wound healing status, condition of surrounding skin, signs of infection, and local pain levels.
- The number of device related (AEs) associated with each of the test dressings.
- Subject-centric outcomes between three treatment groups.

Health Economics Endpoint

To retrospectively compare resource-use as related to:

- Quantity of dressing changes per week (stratified by wound type)
- Time required per dressing change (in minutes)
 - a. Start time: Initiation of old dressing removal
 - b. End time: New dressing is securely in place
- Staff cost associated with dressing change
 - a. Identification of those involved with dressing change (e.g., MD, Nurse, Assistant, etc.)
 - b. Average hourly rate for those individuals directly involved with dressing change (this can be market data if individuals do not want to provide actual salary information)
- Material Cost
 - a. Quantity of each product (dressing) used per week
 - b. Size of dressings used
 - c. Cost of each dressing used per week
 - d. Other material cost used in dressing change
 - i. Identification of products used per week
 - ii. Quantity of each product used per week
 - iii. Cost of each product used per week

Additional Safety Measures

- The incidence of AEs and serious adverse events (SAEs) associated with each of the test dressings.

Study Design

Investigation Code **MxBFlex_02** **Final Version** **Approval date** **2018-06-19****Central Amendment 1 Approval date** **2018-11-08****Central Amendment 2 Approval date**

Prospective, randomized, controlled clinical trial (RCT) using a cross-over (repeated measures) design to evaluate safety and efficacy. The study will be conducted at multiple sites in an outpatient setting.

Each subject will be randomly assigned to one of four treatment groups. The treatments and treatment schedule are detailed in the table below:

	Treatment Group 1	Treatment Group 2	Treatment Group 3	Treatment Group 4
Week 1	Tr. B	Tr. A	Tr. C	Tr. A
Week 2	Tr. B	Tr. A	Tr. C	Tr. A
Week 3	Tr. A	Tr. B	Tr. A	Tr. C
Week 4	Tr. A	Tr. B	Tr. A	Tr. C

*A=Study Product, B=Comparator Product 1, C=Comparator Product 2

Approximately 40 subjects will be enrolled to have 32 subjects for the evaluation. There will be two subject groups: those with VLU and those with DFU. Approximately 50% of the subjects will be in the VLU group and 50% of the subjects in the DFU group. Treatment sequence will be randomized so that a fair distribution is achieved. The total duration of the study will be approximately 4 weeks or 28 ± 2 days.

Visit Schedule

Potential study subjects will be screened for eligibility. Inclusion and exclusion criteria, vital signs, medical record reviews, subject demographics and informed consent will be performed and obtained at the Screening Visit (Day 0). If the patient meets the eligibility criteria, he or she will be enrolled and randomized into one of four treatment groups. The test wound dressing will be applied on the screening day (Day-0) and evaluations will take place twice weekly throughout the 4-week Treatment Period. The dressing will only be changed at Day 7 of each treatment week (e.g. Visit Days 7, 14, 21 and 28) or as needed at the discretion of the study doctor or investigator. There will be a total of 8 visits to the Vascular and Wound Care Center during the Treatment Period. During those visits, evaluations will be performed to assess the condition of the wound dressing, the wound, wound pain and patient comfort.

All study evaluations will be performed by a study doctor or nurse during the follow-up visit at the Vascular and Wound Care Center.

All subjects in the VLU group will receive the same compression therapy and all subjects in the DFU group will receive the same off-loading footwear throughout the entire study period.

Study Methods

Investigation Code	MxBFlex_02	Final Version	Approval date	2018-06-19
		Central Amendment 1	Approval date	2018-11-08
		Central Amendment 2	Approval date	

- Wound dressings will be evaluated twice weekly by the study doctor or study nurse. All other evaluations will be performed once weekly before dressing change.
- There may be an initial debridement (at the investigator's discretion prior to enrollment).
- Additional debridement is not allowed.
- Wound dressing wear time and durability will be determined by study doctors' judgement and by photography.
- Exudate absorption and exudate dispersion will be determined clinically and by photodigital planimetry.
- Wound surface area will be measured serially using photo-digital planimetric software.
- Wound and surrounding skin characteristics will be evaluated by the study doctor at dressing change.
- Dressing comfort and subject-centric outcomes will be captured at the end of weeks 2 and 4.
- SF12 will be captured at the on Day 0 Screening & Baseline Visit and bi-weekly thereafter. Please see Appendix E for sampling of questions.
- Local wound pain will be evaluated using the Baker-Wong (Faces) Scale before and after each dressing change.

Inclusion Criteria

1. Male and female subjects 18-85 years of age with leg and foot ulcers (i.e. VLU, DFU).
2. Subject's Ankle-Brachial Index (ABI) by Doppler is ≥ 0.7 .
3. The subject has adequate circulation to the foot to allow for healing. This must be demonstrated by methods described in Section 4.3.3
4. Signed informed consent.
5. Subject and/or caregiver must be willing and able to tolerate multi-layered compression bandages when applicable and offloading footwear.
6. Study subject must be available and able to visit the clinic twice weekly for the full 4-week period.

Exclusion Criteria

1. Pressure injury (as defined by the National Pressure Ulcer Advisory Panel [NPUAP]) in any anatomical location

Investigation Code	MxBFlex_02	Final Version	Approval date	2018-06-19
		Central Amendment 1	Approval date	2018-11-08
			Central Amendment 2	Approval date

2. Presence of local wound infection as determined by study doctor based on clinical signs and symptoms
3. Subject's ABI is <0.7 or has any evidence of peripheral arterial disease (PAD).
4. Subject diagnosed with malignancy other than cutaneous basal cell carcinoma.
5. Subject has received growth factor therapy (e.g. autologous platelet-rich plasma gel, becaplermin, bilayered cell therapy, dermal substitute, extracellular matrix) within 2 weeks of screening date.
6. Pregnancy or lactation at time of study participation.
7. Subject is currently receiving or has received radiation or chemotherapy within 3 months of randomization.
8. Subject is currently enrolled or participated in another investigational device, drug or biological trial within 30 days of baseline of this study.
9. Present history of alcohol or drug abuse.
10. Known allergy/hypersensitivity to any of the components of the dressing.
11. Subject not suitable for the investigation according to the investigator's judgment.

Investigation Code	MxBFlex_02	Final Version	Approval date	2018-06-19

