4. INVESTIGATION PLAN AND PROCEDURES

4.1 Overall Design and Flow Chart

Study Design

Prospective, randomized, controlled clinical trial (RCT) using a 2x2 cross-over (repeated measures) design to evaluate safety and efficacy. The study will be conducted in an outpatient setting of an academic clinical center.

Each subject will be randomly assigned to one of four treatment groups. The treatments and treatment schedule are detailed in the table below:

Table 1. Treatment Groups

	Treatment Group 1	Treatment Group 2	Treatment Group 3	Treatment Group 4
Week 1	Tr. B	Tr. A	Tr. C	Tr. A
Week 2	Tr. B	Tr. A	Tr. C	Tr. A
Week 3	Tr. A	Tr. B	Tr. A	Tr. C
Week 4	Tr. A	Tr. B	Tr. A	Tr. C

*A=Study Product, B=Comparator Product 1, C=Comparator Product 2

Approximately 40 subjects will be enrolled to have 32 subjects for the evaluation. Approximately 50% of the subjects will be in the VLU group and 50% of the subjects in the DFU group. Treatment sequence will be randomized so that a fair distribution is achieved. The total duration of the study will be approximately 4 weeks or 28 ± 2 days.

Visit Schedule

Potential study subjects will be screened for eligibility. Inclusion and exclusion criteria, vital signs, medical record reviews, subject demographics and informed consent will be performed and obtained at the Screening Visit (Day 0). If the patient meets the study eligibility criteria, he or she will be asked to sign consent. Study subjects will be randomized into one of four treatment groups. The test wound dressing will be applied at screening (Day-0) and evaluations will take place twice weekly throughout the Treatment Period. The scheduled dressing change will be on Day 7 of each treatment week (e.g. Visit Days 7, 14, 21 and 28), unless a dressing change is necessary because of strikethrough loss of adherence or discomfort. There will be a total of 8 visits to the Wound Care Center during the Treatment Period. During those visits, evaluations will be performed to assess the condition of the wound dressing, the wound, wound pain and patient comfort.

Investigation Code	MxBFlex_02	Final Version	Approval date	2018-06-19
		Central Amendment 1	Approval date	2018-11-08
		Central Amendment 2	Approval date	

All study evaluations will be performed by a study doctor or nurse during the follow-up visit at the Wound Care Center.

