All subjects in the VLU group will receive the same compression therapy and all subjects in the DFU group will receive the same off-loading footwear throughout the entire study period.

Study Methods

- Wound dressings will be evaluated twice weekly by the study doctor or study nurse. All other evaluations will be performed once weekly before dressing change.
- There may be an initial debridement (at the investigator's discretion prior to enrollment).
 - Additional debridement is not allowed.
- Wound dressing wear time and durability will be determined by study doctors' judgement and by photography.
- Exudate absorption and exudate dispersion will be determined clinically and by photodigital planimetry.
- Wound surface area will be measured serially using photo-digital planimetric software.
- Wound and surrounding skin characteristics will be evaluated by the study doctor at dressing change.
- Dressing comfort and subject-centric outcomes will be captured at the end of weeks 2 and 4.
- SF12 will be captured at the initial visit and then bi-weekly
- Local wound pain will be evaluated using the Baker-Wong (Faces) Scale before and after each dressing change.

Investigation Code MxBFlex_02 Final Version Approval date 2018-06-19
Central Amendment 1 Approval date 2018-11-08
Central Amendment 2 Approval date

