4.2 Procedures and Assessments

4.2.1 Schedule of Assessment

Table 2. Schedule of Assessment

Assessments	Screening & Baseline Visit (Day 0)	Treatment Phase							
		Week 1 Day 3 (-1/+2)	Week 1 Day 7 (-1/+2)	Week 2 Day 10 (-1/+2)	Week 2 Day 14 (-1/+2)	Week 3 Day 17 (-1/+2)	Week 3 Day 21 (-1/+2)	Week 4 Day 24 (-1/+2)	Week 4 Day 28 (-1/+2)
Inclusion/Exclusion Criteria	✓								
Informed Consent	✓								
Subject ID	✓								
Subject Randomization	✓								
Subject Demography	✓								
Medical/Surgical History	✓								
Vascular Studies ABI, Duplex, PVR, Toe Pressures	✓								
Wound Assessment	✓		✓	✓	✓	✓	✓	✓	✓
Performance of the Dressing		✓	✓	✓	✓	✓	✓	✓	✓
Dressing Application	✓		✓	✓	✓	✓	✓		
Application of Compression Bandages or Off-Loading Footwear	✓	✓	✓	✓	✓	✓	✓	✓	✓
Dressing Removal			✓	✓	✓	✓	✓	✓	✓
Dressing change (if needed) ₂		✓	✓	✓	✓	✓	✓	✓	✓
Concomitant medication	✓	✓	✓	✓	✓	✓	✓	✓	✓
Pain Assessment	✓		✓	✓	✓	✓	✓	✓	✓
Photo of the wound	✓	✓ ₅	✓	✓ ₅	✓	✓ ₅	✓	✓ ₅	✓
Photo of dressing in situ	✓	✓ ₄	✓ ₄	✓ ₄	✓ ₄	✓ ₄	✓ ₄	✓ ₄	✓ ₄
Photo of dressing	✓	✓ ₅	✓	✓ ₅	✓	✓ ₅	✓	✓ ₅	✓
Subject-Centric Outcomes					✓				✓

Investigation Code	MxBFlex_02	Final Version	Approval date	2018-06-19
		Central Amendment 1	Approval date	2018-11-08
			Central Amendment 2	Approval date

Health related quality of life SF12	√					√				√
Reason for Termination			√ ₆							
AE/ADE/SAE/SADE /DD	√		√	√	√	√	√	√	√	√

1 make sure subject is still eligible

2 dressing change to be performed if there is strikethrough of exudate, i.e. loss of edge seal or adherence, leakage, dislodgement, etc.

3 after dressing is applied

4 after outer dressing/compression is removed and before investigational dressing is removed (i.e. 2 photos where applicable)

5 if dressing is changed only

6 if subject is terminated for reasons other than study completion

In case of an unscheduled study visit, safety parameters will be assessed as well as parameters related to the wound status and dressing change.

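### Table 2 shows dressing removals at Days 10, 17 and 24 that the visit schedule does not plan, and the primary endpoint is dressing wear time

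*Combined protocol and SAP*

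**What the plan says.** Two places in the text describe the same schedule. The synopsis (Visit Schedule) states: "The dressing will only be changed at Day 7 of each treatment week (e.g. Visit Days 7, 14, 21 and 28) or as needed". Section 4.1 (Visit Schedule) gives the same days and the exceptions: "e.g. Visit Days 7, 14, 21 and 28), unless a dressing change is necessary because of strikethrough loss of adherence or discomfort".

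Table 2 (Section 4.2.1) differs:

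- The row "Dressing Removal" is ticked at Days 7, 10, 14, 17, 21, 24 and 28.
- The row "Dressing Application" is ticked at Days 0, 7, 10, 14, 17 and 21.
- A separate row, which begins "Dressing change (if needed", is ticked at every visit from Day 3 to Day 28. Its footnote 2 reads: "dressing change to be performed if there is strikethrough of exudate, i.e. loss of edge seal or adherence, leakage, dislodgement, etc".
- The wound-photo and dressing-photo ticks at Days 3, 10, 17 and 24 carry footnote 5: "if dressing is changed only".

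Section 4.1 (Study Methods) has the dressing evaluated twice a week and adds: "All other evaluations will be performed once weekly before dressing change". Table 2 nevertheless ticks Wound Assessment and Pain Assessment at Days 10, 17 and 24 as well.

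**The concern.** The primary endpoint is wear time in days, so the removal schedule limits the wear that can be observed. A dressing taken off intact at a scheduled visit has its wear time cut short by the calendar, not by its own failure.

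The primary analysis (Sections 4.8.1 and 4.8.2) compares the Period 2 minus Period 1 difference between the two sequences. If the removal row is followed, the nominal ceiling is longer in Period 1 than in Period 2. The synopsis plans multiple sites, so different sites could also follow different parts of the document. Each cross-over has 16 subjects and is planned for a half-day difference at 80% power, which leaves little slack.

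The health-economics endpoint is exposed too. It counts dressing changes and dressings used per week, and from week 2 the removal row plans two removals a week where the text plans one, whichever dressing is worn.

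**Working it through.** **1. The two schedules side by side**

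| | Text (synopsis, Section 4.1) | Table 2 |
|---|---|---|
| Removals | Days 7, 14, 21, 28: 4 | Days 7, 10, 14, 17, 21, 24, 28: 7 |
| Removals by period | 2 and 2 | 3 and 4 |
| Applications | Days 0, 7, 14, 21: 4 | Days 0, 7, 10, 14, 17, 21: 6 |
| Nominal intervals, Period 1 | 7, 7 | 7, 3, 4 |
| Nominal intervals, Period 2 | 7, 7 | 3, 4, 3, 4 |

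Both disputed rows have 9 cells, which match the 9 visit columns. No shift of columns turns 7 removals into 4.

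**2. Can the extra ticks be the changes made for need?** No. Those have their own row, which includes Day 3, where the removal row is blank. Footnote 5 treats a mid-week change as conditional, while the removal row shows no condition. At Day 24 a dressing is removed and none is applied, yet a removal is ticked again at Day 28.

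**3. Visit windows.** Every visit after Day 0 has a window of -1/+2 days. The nominal 4-day interval from Day 17 to Day 21 can therefore run from Day 16 to Day 23, which is 7 days. The nominal intervals are not hard ceilings.

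**4. The plan's own sample size (Section 4.8.3).** The expected contrast between sequences is 2 × 0.5 = 1.0 day and the SD of the period difference is 0.65. The normal formula gives n per sequence = 2 × (1.960 + 0.842)² × 0.65² / 1.0² = 6.6, so 7. The t-based calculation gives 7.72, so 8 per sequence and 16 in total, with 81.6% power. The plan's 16 is reproduced.

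**5. Illustration of the effect.** From the documents: difference 0.5 day, SD 0.65, 8 + 8 subjects, two-sided 5%. Assumed: normal wear times; within-period SD 0.65/√2 = 0.46; one wear time per period, cut at the longest interval in that period; between-subject SD 0 to 1 day; comparator mean 3, 4 or 5 days; a two-sample t-test in place of the permutation test. In the window case the visit offsets are drawn uniformly over -1 to +2 days.

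| Power (%), between-subject SD 0 to 1 | Mean 3 | Mean 4 | Mean 5 |
|---|---|---|---|
| All follow the text (ceilings 7 and 7) | 81–82 | 82 | 82–80 |
| All follow the row, with visit windows | 82–77 | 77–63 | 51–37 |
| All follow the row, fixed ceilings 7 and 4 | 82–66 | 68–36 | 53–19 |

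At a mean of 5 days the true 0.5-day difference appears as about 0.37–0.38 day with windows, and as 0.25–0.27 day with fixed ceilings. At a mean of 2 days power is 82–78% even with fixed ceilings, so there is little loss. With fixed ceilings, type I error stays between 0.046 and 0.053. An exact permutation test with fixed ceilings gave similar power, for example 52% at mean 5 and between-subject SD 0.

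A mix of practices can cost more than uniform following. With fixed ceilings, mean 5 and between-subject SD 0, power is 37% if half the subjects follow the row and 53% if all do.

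**The case against.** The best case against giving this weight is that sites would probably not follow the removal row to the letter. The synopsis restricts changes to the weekly visits or need, Section 4.1 agrees, footnotes 2 and 5 make mid-week changes conditional, and the row breaks down at Day 24. This stands: following by every subject is an extreme case, and the documents give no basis for estimating how many sites would do so.

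A second objection is that the absence of a condition is not certain. Footnotes 1 and 3 are defined under Table 2, but in the PDF text as read no row carries their markers, so a marker could be missing from the removal row too. This stands as a caveat. It does not affect the count of 7 ticks against 4 planned days, or the separate row for changes made for need.

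A reader might infer three stronger things, none of which the documents support.

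- *Power collapses to below 20%.* That figure needs a fixed 4-day ceiling in Period 2, which the visit windows contradict, together with a mean of 5 days, a between-subject SD of 1 day and following by every subject. The documents give none of these.
- *The conflict favours one dressing.* The same ticks apply in all four sequences, and type I error stays near 5% in the illustration.
- *Only power is lost and the estimate is unbiased.* Section 4.8.2 reports the mean difference with a confidence interval, and cutting wear times short pulls that difference toward zero.

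**Conclusion.** The inconsistency is real and rests on counts alone: 7 removals and 6 applications in Table 2, against 4 and 4 in the text, plus an unmatched removal at Day 24. It needs no statistical assumption beyond the caveat about footnote markers.

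Its effect is conditional. Where the removal row is followed, the wear-time difference is attenuated, power against 0.5 day falls, and dressing changes per week partly measure the schedule. The size cannot be determined, because the documents give no expected wear times, no between-subject SD, no rule for which dressing of a period counts, no rule for scoring an intact dressing removed on schedule, and no indication of how many sites would follow the row. The illustration suggests a negligible effect for short wear times and a material one for wear times of about 4 to 5 days or more. Those power figures indicate direction and order of size; they are not estimates for this trial.

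**What to change.** Reconcile the Dressing Removal and Dressing Application rows of Table 2, including Day 24, with the Visit Schedule in the synopsis and in Section 4.1. At the same time check the Wound Assessment and Pain Assessment rows against the once-weekly rule in Section 4.1 (Study Methods). Then issue one clarification so that all sites follow a single schedule. Which schedule is right is for the sponsor to decide; this point takes no position on it.

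The cost is an edit to the passages concerned and one note to sites. The reconciliation itself requires no change to the sample size or the analysis method.

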LIST OF APPENDICES

- Appendix A *Signatures of Clinical Investigation Plan*
- Appendix B *Package inserts of all study dressings*
- Appendix C *Case Report Forms template (CRF)*
- Appendix D *Patient Informed Consent Form (ICF)*
- Appendix E *SF12 questionnaire, Questionnaire for the subjects*

LIST OF ABBREVIATIONS

ADE	Adverse Device Effect
AE	Adverse Event
CA	Competent Authority
CIP	Clinical Investigation Plan
CRF	Case Report Form
CTA	Clinical Trial Agreement
DD	Device Deficiency
DFU	Diabetic Foot Ulcer
EC	Ethics Committee
eCRF	Electronic Case Report Form
FAS	Full Analysis Set
ICF	Informed Consent Form
IRB	Institutional Review Board
NPUAP	National Pressure Ulcer Advisory Panel
PAD	Peripheral Arterial Disease
PCG	Pharma Consulting Group
PP	Per Protocol
SAE	Serious Adverse Event
SADE	Serious Adverse Device Effect
SD	Standard Deviation
UADE	Unanticipated Adverse Device Effect

Clinical Investigation Plan

Document ID: PD-545909 Rev: 01

Title: CIP_MxBFlex_02 with Integrated Central Amendment 1 and 2

Page 11(42)

Investigation Code **MxBFlex_02** Final Version Approval date **2018-06-19**

Central Amendment 1 Approval date **2018-11-08**

Central Amendment 2 Approval date

VLU **Venous Leg Ulcer**

Investigation Code	MxBFlex_02	Final Version	Approval date	2018-06-19
		Central Amendment 1	Approval date	2018-11-08
		Central Amendment 2	Approval date	

